## **19.0 Provisions to Protect the Privacy Interests of Subjects**

A number of data integrity procedures will be used to ensure the validity and integrity of the data and the safety of all participants involved in the study. All procedures involving human participants will be performed at the PI's laboratory at FSU. Relevant data and safety information obtained from each study participant will be verified against the original source documents by the study coordinator, and any identified discrepancies will be reviewed at the weekly meetings. All identifying information will be archived on a password-protected server in password-protected folders and files. Only study staff will have access to these files. We will use the double data entry module in REDCap for self-report data (e.g., questionnaires).

Computer-generated reports of variable frequencies and participant lists will be reviewed, leading to possible corrections to coding or entry. After data within a given group are checked for accuracy, the data will be stored in the password-protected folders.

Adherence to the study protocol will be promoted throughout the trial. Of note, the research team will receive proper training using detailed manuals of procedures for all aspects of the proposed research, including treatment protocols and participant interaction, in a step-by-step fashion. All study personnel will be trained before study initiation, and the PI will carry out weekly supervision of the research team's adherence to protocols. These procedures were successfully implemented in our previous studies.

## **20.0 Compensation for Research-Related Injury**

This study poses minimal risks because (1) the discomfort is transient in nature and generally subsides immediately after the procedure; (2) participants are instructed that they may stop any procedure at any time with no adverse consequences; and (3) the level of discomfort experienced by participants is below their tolerance level. Also, risks will be minimized by adhering to our exclusion criteria, and the study physician will have full discretion to exclude participants who may be at excessive risk. There will be no compensation in the event of research related injury.

## **21.0 Economic Burden to Subjects**

There will be no costs that subjects may be responsible for because of participation in the research.

## **22.0 Consent Process**

Subjects will participate in the study only after they provide verbal and signed consent. MMSE will be used to exclude people with severely diminished cognitive function (i.e., MMSE score  $\leq 15$ ), and we will get the consent from the subject whose MMSE score is above 15. In addition to the MMSE cutoff, to ensure participant understanding of the study procedures, participants will be required to accurately describe the purpose and

requirements of their participation in the study following review of the informed consent form.

## **23.0 Process to Document Consent in Writing**

Trained research personnel will obtain consent in a private room where participants feel comfortable. Informed consent will be documented in writing via the participants' and investigators' signatures.

## **24.0 Setting**

The research team will conduct the research at the PI's research lab at the FSU.

## **25.0 Resources Available**

This study, funded by NIH, was approved by the IRB at the University of Texas Health Science Center at Houston. On this R15 project, all the data will be collected at the [name] laboratory at FSU. Adequate equipment and resources are available in the [name] laboratory to carry out the procedures and accommodate the personnel described in this proposal.

## **26.0 Multi-Site Research**

N/A

## Statistical Analysis Plan (SAP)

A standard randomized controlled design will be adopted in this study, and we will randomly assign 40 patients to either active tDCS or sham tDCS (20 per group). Our primary analysis will compare clinical pain changes from baseline to the final intervention session between the active tDCS and sham tDCS groups. We plan to conduct 2 hypothesis tests for the main outcomes (MOBID-2 and fNIRS at Day 5) at a family-wise significance level of  $\alpha = 0.025$  after Bonferroni correction. With the sample size 20 per group, we will be able to detect the expected effect size of 1.0 with 80% power at a significance level of 0.025.

All data will be analyzed using the intention-to-treat approach. All demographic and clinical variables will be summarized using descriptive statistics, such as mean  $\pm$  standard deviation or median (interquartile range) as appropriate for continuous variables and frequency and percentage for categorical variables. The distribution of all variables will be examined to check the validity of distribution assumptions before any analysis, using measures of central tendency and a visual inspection of histograms and quantile-quantile plots. If the assumption of normality is not met, nonparametric approaches will be employed. SAS 9.4 (SAS Institute, Cary, NC) will be used to perform the proposed statistical analyses.

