randomized, sham-controlled, parallel group (1:1 for two groups) pilot clinical trial. The central hypothesis is that home-based, remotely supervised tDCS will decrease pain. This hypothesis will be tested by pursuing the following specific aims: evaluate the preliminary effects of home-based M1-SO applied tDCS on clinical pain in persons with early-stage ADRD (specific aim 1); evaluate the preliminary effects of home-based M1-SO applied tDCS on pain related cortical response in persons with early-stage ADRD (specific aim 2); and evaluate the feasibility and acceptability of home based M1-SO-applied tDCS for pain management in persons with early stage ADRD (specific aim 3). We will also obtain data, as an exploratory aim, to investigate whether tDCS reduces behavioral and psychological symptoms of dementia. The proposed study will directly investigate the effects of home-based, remotely supervised tDCS in 40 persons with ADRD using an experimenter- and participant-blinded, randomized, sham-controlled, parallel group (1:1 for two groups) pilot clinical trial. Caregivers will set up and administer home-based tDCS for persons with ADRD and must be present at each home-based session, and participants will be remotely supervised by trained research staff at each stimulation to ensure the use of proper technique. Primary outcome (clinical pain assessed by the MOBID-2) will be performed by the caregivers. Caregivers will be trained at the in-person baseline visit to use tDCS devices and to perform outcome measures. tDCS session will be not performed if the caregiver is not available, and it needs to be the same caregiver throughout the trial. The proposed research is significant because it is expected to provide valuable insight into an exciting new modality of nonpharmacological pain management that is easy, safe, and noninvasive with minimal side effects.

Participants will do remotely-supervised tDCS at their home or private room for 5 days under real time supervision by the research staff. Data will be collected by study staff across several points using equipment and resources available at [name] (PI's) laboratory at Florida State University (see Table below). The primary endpoint will be clinical pain (MOBID-2) collected after the final intervention session. Participants will visit Florida State University two times, and each visit will take approximately 2 hours.

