Research subjects/caregivers will be called one day prior to their scheduled study visit and asked a series of COVID-19 related questions covering topics such as isolation and quarantine, vaccination status, symptoms, test results, and exposure. And then subjects will be notified about the FSU COVID-19 precautions. Consent materials will be modified to include a statement to the effect that no in-person activity may involve any individual (human research participants (human subjects) or study staff—vaccinated or unvaccinated) who (1) tests positive for COVID-19 or (2) has been in close contact with someone who has COVID-19, within at least the past 10 days of the positive COVID-19 test or close contact; that prospective subjects will be screened for this purpose; and that for any in-person research activity the use of masks is strongly recommended (and may be required in certain locations) as is a full COVID-19 vaccination.

Table 1. Timetable for Collection of Data

		Week 1	F1	F2	F3
--	--	--------	----	----	----

Stimulation Session	Baseline	1	2	3	4	5			
MMSE	X								
Medical History Questionnaire	X								
Clinical Pain (MOBID-2): primary outcome	X	X	X	X	X	X	X	X	X
Clinical Pain (NRS): secondary outcome	X	X	X	X	X	X	X	X	X
BPSD (CMAI, NPI): secondary outcome	X					X	X	X	X
Pain-related cortical response (fNIRS): secondary outcome	X					X			
tDCS experience questionnaire: secondary outcome						X			
Patient satisfaction (CSQ-8): secondary outcome						X			
Side effects questionnaire: secondary outcome		X	X	X	X	X			

Note: F, Weekly follow-up phone assessment after completion of tDCS treatment; MMSE, Mini-Mental Status Exam, MOBID, Mobilization-Observation-Behavior-Intensity-Dementia Pain Scale; BPSD, behavioral and psychological symptoms of dementia; CMAI, Cohen-Mansfield Agitation Inventory; fNIRS, functional near-infrared spectroscopy; CSQ, Client Satisfaction Questionnaire.

- MMSE. MMSE will be used to exclude people with severely diminished cognitive function (i.e., Mini-MentalStatus Exam score  $\leq 15$ ).
- Medical History Questionnaire. All participants will complete a thorough questionnaire to collect demographic and medical history details, including age, sex, height, weight, duration of knee OA, current and past treatments for knee OA, comorbid conditions, and current medications.

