- A multichannel fNIRS imaging system (LIGHTNIRS, Shimadzu, Kyoto, Japan) will be used to determine changes in regional cerebral blood flow in response to thermal stimuli applied to the right forearm of participants. The illumination and detection optodes will be arranged in a geometrical layout that will cover the prefrontal and somatosensory cortex regions bilaterally, consistent with locations investigated in previous studies. For evoked pain scans, low-intensity thermal stimuli at the thermal pain threshold level will be applied for a few seconds during multiple scanning runs, followed by an approximately equivalent interval of no stimulation, which is commonly used in pain related neuroimaging studies since thermal hyperalgesia is an important component of chronic pain. A temperature-controlled pain generator (Medoc TSA-II Neurosensory Analyzer) will be used to produce thermal stimulation through a 16 mm  $\square$  16 mm thermode. We expect to observe reduced pain-evoked activation in the active tDCS group in the prefrontal and somatosensory cortices. To minimize the inconvenience to participants, we will deliver thermal stimuli that are below the individual's pain tolerance level and set the cutoff temperature at 50°C. These procedures will ensure maximum patient safety and comfort while allowing successful and reliable imaging of the pain-related cortical response.

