## **10.0 Inclusion and Exclusion Criteria\***

A maximum of 40 persons with early-stage Alzheimer's disease and related dementias (ADRD) will be enrolled. Participants who are 50 to 90 years old will be considered eligible if they (1) have early- stage ADRD, (2) have caregiver-reported chronic pain (average pain in the past 3 months  $\geq$  3 out of 10), (3) have a caregiver willing to participate in the study who sees the participant at least 10 hours/week, (4) can speak and read English, and (5) have no plans to change medication regimens during the trial. The diagnosis of early-stage ADRD will be verified by PI based on Mini-Mental Status Exam score (generally 16-23), the blind/telephone version of the Montreal Cognitive Assessment (MoCA, generally 16-26), or Clinical Dementia Rating scores (generally 0.5-1.0). We will assess the use of medications that can influence responses to tDCS (e.g., selective serotonin reuptake inhibitors, beta-blockers) and include them as covariates in our statistical models. Participants will be excluded if they have any concurrent medical conditions that could confound the interpretation of outcome measures, pose a safety risk for any of the assessment or tDCS procedures, or preclude the successful completion of the protocol. Specific exclusion criteria are: (1) history of brain surgery, brain tumor, seizure, stroke, or intracranial metal implantation, (2) alcohol/substance abuse, (3) severely diminished cognitive function (i.e., Mini-Mental Status Exam score  $\leq$  15), and (4) hospitalization within the preceding year for neuropsychiatric illness. Participants who do not have a device with internet access will be provided a smartphone to use during the study.

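### The primary analysis compares change in MOBID-2 and calls for no baseline adjustment; an ANCOVA on the baseline score already collected would be a better primary model at very small cost

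*SAP*

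**What the plan says.** The SAP's first paragraph gives the primary analysis as "Our primary analysis will compare clinical pain changes from baseline to the final intervention session between the active tDCS and sham tDCS groups". The outcome is MOBID-2: Protocol section 6.0 states that "The primary endpoint will be clinical pain (MOBID-2) collected after the final intervention session", and the SAP lists MOBID-2 at Day 5 as one of its two tested outcomes. The SAP names no model, baseline term or covariate for this comparison.

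The baseline value is available. In Table 1 of Protocol section 6.0, the row "Clinical Pain (MOBID-2): primary outcome" is marked at baseline, at each of the five sessions and at the three follow-ups.

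The sample size statement, made for an alpha of 0.025, reads "With the sample size 20 per group, we will be able to detect the expected effect size of 1.0 with 80% power".

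The only mention of covariates is in Protocol section 10.0, which undertakes to assess "medications that can influence responses to tDCS (e.g., selective serotonin reuptake inhibitors, beta-blockers) and include them as covariates in our statistical models". The SAP does not take this up. The data exist, because the medical history questionnaire in section 6.0 records "comorbid conditions, and current medications".

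**The concern.** Subtracting the baseline score is the same as adjusting for it with a slope fixed at 1. If the true slope of Day-5 score on baseline is below 1, as it usually is when a measure regresses to the mean, the subtraction over-corrects. The arm that happens to start with more pain then tends to show the larger fall even when treatment does nothing.

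In a large trial, chance differences at baseline are negligible. With 20 per arm they are not. The two things at stake are how far the primary result depends on the luck of the allocation, and some precision. Both can be improved with data that the trial already collects.

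**Working it through.** **Inputs from the documents.** 20 per arm, effect size 1.0, significance level 0.025 (SAP).

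**Assumptions.** The test is two-sided, 0.025 is the level for each test, and the effect of 1.0 is in SDs of the change score. The documents give neither the correlation rho between baseline and Day-5 MOBID-2 nor the SDs, so ranges are used. k is the Day-5 SD divided by the baseline SD.

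**1. The plan's own figure.** Two-sample t-test, noncentrality 1.0 × √(20/2) = 3.162, 38 df, two-sided 0.025: power 0.793. A one-sided test would give 0.869. The stated 80% therefore fits an unadjusted two-sided comparison.

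**2. Chance imbalance.** The standard error of the baseline difference is √(2/20) = 0.316 SD. A difference of 0.4 SD is 0.4/0.316 = 1.265 standard errors. The chance of at least this much is 0.103 with active higher, and 0.206 in either direction.

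**3. Error given that imbalance.** With no treatment effect, the expected difference in change is (slope − 1) × 0.4 SD. At rho 0.5 and equal SDs this is −0.20 SD, which looks like pain relief on active. Simulation of 100,000 null trials per rho, k = 1, active arm 0.4 SD higher at baseline (simulation error about 0.05 points):

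| rho | Change score, falsely favours active | Change score, two-sided error |
|---|---|---|
| 0.3 | 3.2% | 3.2% |
| 0.5 | 3.1% | 3.2% |
| 0.7 | 2.8% | 3.0% |
| 0.8 | 2.6% | 2.9% |
| 0.9 | 2.2% | 2.7% |

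The nominal values are 1.25% per direction and 2.5% in total. Baseline ANCOVA falsely favours active in about 1.25% at every rho. In the mirror case, with active 0.4 SD lower, the change-score test falsely favours active in only 0.01% to 0.5%. Averaged over all randomisations the change-score test keeps its level.

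**4. Power of ANCOVA.** The residual variance relative to the change-score variance is R = k²(1 − rho²)/(1 + k² − 2·rho·k). With p covariates, the effective effect is 1/√(R × 37/(37 − p)) on 38 − p df. Example: k = 1, rho 0.5, p = 1 gives R = 0.75, effective effect 1/√(0.75 × 37/36) = 1.139, power 0.892.

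| rho | k = 1, baseline only | k = 1, baseline + 2 indicators | k = 1.25, baseline only |
|---|---|---|---|
| 0.3 | 0.932 | 0.916 | 0.877 |
| 0.5 | 0.892 | 0.871 | 0.828 |
| 0.7 | 0.848 | 0.823 | 0.788 |
| 0.8 | 0.825 | 0.799 | 0.780 |
| 0.9 | 0.802 | 0.775 | 0.802 |

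The comparator is 0.793 throughout. With k = 0.8, baseline-only power is 0.936 or more at rho 0.3 to 0.8.

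**5. The worst case.** The denominator of R minus its numerator is (1 − k·rho)², so R never exceeds 1 and equals 1 only when the slope k·rho is 1. There, power is 0.780 with baseline only, a loss of 0.793 − 0.780 = 1.3 points. With equal SDs, baseline ANCOVA breaks even at rho 0.94, where R = (1 + 0.94)/2 = 0.97. With k = 1.25 it loses only in a band around slope 1. The band opens at rho 0.67 and closes near 0.88, where R = 1.5625 × 0.2256/0.3625 = 0.972, close to the break-even value; by rho 0.9 ANCOVA is ahead again.

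**6. Medication indicators.** Adding two that do not predict pain costs, at k = 1, a further 1.6 (rho 0.3) to 2.7 points (rho 0.9). At slope 1 power is 0.752, which is 4.1 points below the unadjusted test.

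**The case against.** The strongest defence is that nothing here is wrong. A change-score comparison is unbiased under randomisation, the power claim holds, and this is a 40-person pilot of preliminary effects. The SAP does not exclude ANCOVA either. All of that stands.

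The power gain may also be slight. Section 6.0 has caregivers perform the MOBID-2 and says of the caregiver that "it needs to be the same caregiver throughout the trial", so a high correlation is plausible. At rho 0.8 to 0.9 with equal SDs the gain is 1 to 3 points. This also stands, and the case does not rest on power alone.

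A reader might infer more from the tables than they show:

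- **That the planned test inflates type I error.** It does not. The excess is conditional on one direction of imbalance and is offset in the other.
- **That the Protocol and SAP contradict each other on covariates.** They do not. The SAP is silent, and section 10.0 does not say which model the medications enter.
- **That the result is left open to choice after the data are seen.** The unnamed model, the open medication list and the unnamed nonparametric fallback are missing detail. The documents do not show that the analysis would be selected on its result.

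The pilot argument carries less weight. The SAP plans formal, multiplicity-corrected tests with a power statement, so the choice of primary model matters even at this size.

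**Conclusion.** The point holds as an inexpensive improvement to a valid analysis. The primary comparison fixes the baseline slope at 1 and leaves the result exposed to chance imbalance. For an active arm starting 0.4 SD higher, the two-sided error is 2.7% to 3.2% instead of 2.5%, and at low rho almost all of it favours active. Baseline ANCOVA removes that dependence, and its power lies between a small loss and a worthwhile gain over 0.793.

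The power figures rest on assumed values of rho and the SD ratio, and on reading the effect size as change-score SDs. The bound of 1.3 points on the loss does not depend on rho or the SD ratio. The error figures assume equal SDs.

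The point is confined to MOBID-2. For fNIRS, the optodes are "arranged in a geometrical layout that will cover the prefrontal and somatosensory cortex regions bilaterally" and no single summary measure is named, so how to adjust it for baseline is a separate question.

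**What to change.** In the SAP, replace the primary comparison with an ANCOVA of Day-5 MOBID-2 on treatment group, with baseline MOBID-2 as a continuous covariate. Report the adjusted group difference with its confidence interval. The unadjusted comparison of changes can be kept as a supporting analysis.

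Put the medication covariates of Protocol section 10.0 in a sensitivity model, as a short closed list with its coding, fixed before unblinding. In the primary model, two non-prognostic indicators would cost about 2 to 3 points of power beyond the baseline term.

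The cost is SAP wording and one degree of freedom. No new data are needed. The price is at most 1.3 points of power, paid only if the true slope is near 1, for example at an SD ratio of 1.25 with rho near 0.8.

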
Therefore, we will examine the effect of tDCS in persons with ADRD. Our hypothesis is that remotely supervised tDCS at home will decrease clinical pain.

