## **12.0 Local Number of Subjects**

The number of subjects who are expected to be enrolled and screened is 24, and the number of subjects needed to complete the research procedures (i.e., numbers of subjects excluding screen failures.) is 20. The total number of subjects to be accrued locally is 20, since we completed data collection for 20 subjects at the University of Texas Health Science Center at Houston before PI ([name]) moved to Florida State University.

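### The SAP labels 0.025 family-wise for two Bonferroni tests but computes power at an undivided 0.025; most likely 0.025 is the per-test level, mislabelled

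*SAP*

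**What the plan says.** The first paragraph of the SAP randomizes 40 patients, 20 per group, and sets the error rate for the two main comparisons: "We plan to conduct 2 hypothesis tests for the main outcomes (MOBID-2 and fNIRS at Day 5) at a family-wise significance level of" 0.025. The text continues "after Bonferroni correction. With the sample size 20 per group", and the power claim follows: "we will be able to detect the expected effect size of 1.0 with 80% power at a significance level of 0.025".

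The figure 0.025 therefore appears twice, once as a family-wise level and once as the level at which power was computed. Neither document gives a per-test level of 0.0125, an overall level of 0.05, or the sidedness of the tests. The hypothesis in Protocol section 3.0 is worded in one direction ("Our hypothesis is that remotely supervised tDCS at home will decrease clinical pain"), but no one-sided test is declared.

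**The concern.** A family-wise level is the total error allowed across the family, and Bonferroni divides that total among the tests. If 0.025 is the total for two tests, each test runs at 0.0125 and power should be computed there. If 0.025 is the result of the division, the total is 0.05 and the family-wise label is wrong. The SAP uses the same number in both roles.

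What is at stake is the significance threshold for MOBID-2, the primary outcome. With two-sided tests, a p-value between 0.0125 and 0.025 is significant if 0.025 is the per-test level, and not significant if the family-wise label is applied literally. A threshold that has to be interpreted after the results are known is open to challenge.

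**Working it through.** **Inputs.** From the SAP: n = 20 per group, effect size 1.0, two tests, stated level 0.025, stated power 80%. Assumptions: the effect size is a standardized mean difference (the SAP gives no SD), the test is an unadjusted two-sample t-test, and all 20 per group are evaluable.

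**Formulas.** Degrees of freedom are 2 × 20 − 2 = 38. The noncentrality is d × √(n/2) = 1.0 × √10 = 3.162. Power is the probability that a noncentral t variable with these parameters exceeds the critical value. The normal approximation is Φ(3.162 − z), where z is the critical normal quantile.

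**Step 1: reproduce the stated 80%.** At two-sided 0.025 the critical t is 2.334 and power is 79.3%. A simulation of 400,000 trials gave 79.2%. The normal approximation gives 82.1% power; it needs 19.01 per group for 80%, which rounds up to 20. The SAP's figure is reproduced at an undivided two-sided 0.025.

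**Step 2: apply the family-wise label literally.** Each test runs at 0.025/2 = 0.0125. The two-sided critical t is 2.622 and power is 70.3% (simulation 70.4%; normal approximation 74.7%). The stated 80% is not reproduced.

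**Step 3: compare the candidate readings at d = 1.0, n = 20 per group.**

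| Per-test level | Bonferroni family-wise level | Power, t | Power, normal | n per group for 80% (t / normal) |
|---|---|---|---|---|
| 0.025 two-sided | 0.05 | 79.3% | 82.1% | 21 / 20 |
| 0.0125 two-sided | 0.025 | 70.3% | 74.7% | 24 / 23 |
| 0.0125 one-sided | 0.025 | 79.3% | 82.1% | 21 / 20 |
| 0.025 one-sided | 0.05 | 86.9% | 88.5% | 17 / 16 |

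The first and third rows agree because two-sided 0.025 and one-sided 0.0125 share an upper critical value.

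**Step 4: check the family-wise levels.** If the two tests were independent, the chance of at least one false positive would be 1 − 0.975² = 0.0494 at 0.025 each, and 1 − 0.9875² = 0.0248 at 0.0125 each. Bonferroni bounds these at 0.05 and 0.025 whatever the correlation.

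**Step 5: size of the disputed zone, two-sided.** The smallest significant observed difference is critical t × √(2/20): 2.334 × 0.3162 = 0.74 SD at 0.025, and 2.622 × 0.3162 = 0.83 SD at 0.0125. At a true effect of 1.0 SD, the chance that the p-value lies between 0.0125 and 0.025 is the difference in power, 79.26% − 70.34% = 8.9%. This matters only if someone would actually apply 0.0125.

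**The case against.** The strongest reply is that the paragraph largely explains itself. The level is described as the one reached after Bonferroni correction, the next sentence uses that same number for power, and two-sided 0.025 per test reproduces the 80%. Only the family-wise label points the other way. This reply stands, and it is why the point concerns a label.

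A second reply is that the conflict depends on two-sided testing, which the SAP does not state. This also stands in part. One-sided tests at 0.0125 would have a family-wise level of 0.025 and 79.3% power, and the hypothesis is directional, so the power figure alone cannot exclude that reading. It fits the text less well, because the power sentence gives 0.025 and not 0.0125.

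Two stronger readings are tempting. A reader might infer that the trial is underpowered, with 70.3% where 80% is claimed. The documents do not support that: the shortfall arises only if two-sided 0.0125 per test was intended, and no passage says so. A reader might also infer that the significance threshold itself is wrong. On the likeliest reading, 0.025 per test is a valid Bonferroni level, and only the name given to it is incorrect.

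What the replies do not remove is that the term is wrong for a per-test level, that the overall level appears nowhere, and that sidedness is missing.

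**Conclusion.** The point holds as a labelling error with minor consequences. With two-sided tests, a family-wise level of 0.025 over two Bonferroni tests is incompatible with 80% power at an effect of 1.0 and 20 per group: power would be 70.3%. The likeliest intention is 0.025 per test within a family-wise 0.05. Power is then 79.3%, which is about 80%, and the sample size stands. The 0.05 is an inference from the wording and the reproduced power, since neither document states it.

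The power figures rest on the assumptions listed with the inputs. The SAP names no specific test and allows nonparametric methods, and Protocol section 10.0 puts medication use into the models as covariates, so the final analysis may differ somewhat from the t-test. That would not change the conflict between the label and the level used for power.

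**What to change.** The sponsor should confirm which level was intended.

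- **If it is as inferred,** replace the SAP wording with: *The two-sided family-wise alpha is 0.05; each of the two tests (MOBID-2 and fNIRS at Day 5) is performed at two-sided 0.025 (Bonferroni).* Leave the sample size unchanged and describe power as about 80%.
- **If a family-wise 0.025 was intended,** state sidedness and the per-test level of 0.0125, and restate the power by t-test: 70.3% two-sided or 79.3% one-sided.

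Date the change before treatment codes are linked to outcomes. Protocol section 12.0 reports that half the planned data are already in hand ("since we completed data collection for 20 subjects at the University of Texas Health Science Center at Houston"), so the date of the clarification should be on record.

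The cost is one sentence in the SAP. It adds no patients, visits or measurements, and on the natural reading it leaves the rejection rule as it is.

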- Clinical pain will be measured to rate patients' pain via the Mobilization-Observation-Behavior Intensity-Dementia (MOBID-2) scale from 0 to 10, which will be primary outcome measure for data analysis purposes. The MOBID-2 is a well-validated measure with good ability to detect painchange in persons with ADRD. We also measure clinical pain by asking participants to rate their average pain over the past 24 hours via NRS from 0 (no pain) to 100 (worst pain imaginable), following Initiative on Methods, Measurement, and Pain Assessment in Clinical Trials recommendations for clinical trials involving chronic pain. NRS is appropriate for use among older adults with mild to moderate dementia.
- BPSD. NPI will be used to obtain information on behavioral and psychological symptoms of the patients. NPI comprises 12 items that are summed to yield an overall score of 0-144 (each item will be rated frequency X severity, totaling 0 – 12), with higher scores indicating greater symptoms. We also collect CMAI, which is comprised of 29 items that are summed to yield an overall score of 29-203 (each item will be rated 7-point scale of frequency). Trained research staff will conduct the NPI interview. In terms of training, two raters (one primary and one back-up) conduct mock administrations to each other. Same rater will conduct the assessment with the subjects for fidelity. PI will

- review NPI and CMAI and will not refer subjects for clinical review based on the result.

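### The SAP splits alpha between MOBID-2, the protocol's only primary outcome, and fNIRS, which the protocol labels secondary, and gives no rule for which result makes the trial positive

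*SAP*

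**What the plan says.** Protocol section 6.0 ranks the outcomes in three places, and they agree.

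- The narrative: "The primary endpoint will be clinical pain (MOBID-2) collected after the final intervention session".
- The list of measures, on the MOBID-2 score: "which will be primary outcome measure for data analysis purposes".
- Table 1: "Clinical Pain (MOBID-2): primary outcome" on one row and "Pain-related cortical response (fNIRS): secondary outcome" on another.

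The central hypothesis in the same section concerns pain only. The protocol gives no alpha, multiplicity rule or success criterion. Its study summary (section 1.0) lists the pain aim and the cortical-response aim together under secondary objectives.

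The SAP, first paragraph, begins in agreement with that ranking: "Our primary analysis will compare clinical pain changes from baseline to the final intervention session between the active tDCS and sham tDCS groups". The next sentence reads "We plan to conduct 2 hypothesis tests for the main outcomes (MOBID-2 and fNIRS at Day 5", and sets a level of 0.025, described as family-wise, "after Bonferroni correction". It then claims 80% power for an effect size of 1.0 with 20 per group "at a significance level of 0.025". It does not give the sidedness or an unadjusted overall alpha, nor does it say whether success needs MOBID-2, either test, or both.

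**The concern.** The two documents give fNIRS a different standing, and the SAP does not settle the matter internally: one sentence makes pain the primary analysis and the next gives fNIRS an equal share of the error budget. A Bonferroni split is the usual device when either of two outcomes may carry a claim. Here one of the two is ranked as secondary, so the sole primary outcome is tested at a stricter level to make room for it.

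Two things are at stake. One is power on the pain question, which is the trial's central hypothesis. The other is interpretation. Without a success rule, a null pain result with a positive fNIRS result could be presented as a positive main outcome by someone following the SAP's list, and as a failed primary with a supportive biomarker by someone following Table 1.

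**Working it through.** **Inputs.** From the SAP: 20 per group, standardised effect d = 1.0, level 0.025, stated power 80%. No dropout allowance is given, so none is used. Assumed: two-sided tests and, for the comparison, an overall alpha of 0.05. Neither is stated in either document.

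**Step 1: reproduce the stated power.** For a two-sample t-test with n per group, df = 2n - 2 = 38 and the noncentrality is d x sqrt(n/2) = 1.0 x sqrt(10) = 3.16. At two-sided 0.025 the critical t is 2.334 and the power is 79.3%. The normal approximation gives n = 2 x (2.241 + 0.842)^2 / 1.0^2 = 19.0, rounded up to 20 per group. The SAP's figure therefore reproduces with 0.025 as the two-sided per-test level.

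**Step 2: check other readings of 0.025.**

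- Two-sided, with 0.025 as the family-wise level and 0.0125 per test: 70.3%, which does not match 80%.
- One-sided 0.025 per test: 86.9%, which does not match either.
- One-sided, with 0.025 as the family-wise level and 0.0125 per test: 79.3%. This is the same test in the favourable direction as two-sided 0.025, and removing the split would again give 86.9%.

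**Step 3: type I error.** Two tests at 0.025 sum to 0.05. If they are independent the family-wise error is 1 - (1 - 0.025)^2 = 0.0494. There is no inflation above 0.05.

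**Step 4: what the split costs MOBID-2.** Same formula, with critical t 2.334 at 0.025 and 2.024 at 0.05:

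| True effect (SD) | Power at 0.025 | Power at 0.05 | Cost (points) |
|---|---|---|---|
| 1.0 | 79.3% | 86.9% | 7.6 |
| 0.9 | 69.5% | 79.2% | 9.7 |
| 0.8 | 58.1% | 69.3% | 11.2 |
| 0.5 | 23.8% | 33.8% | 10.0 |

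The effect detectable with 80% power is 1.01 SD at 0.025 and 0.91 SD at 0.05. The n for 80% power at d = 1.0 is 21 and 17 per group. On the literal two-sided family-wise reading the cost at d = 1.0 is similar (79.3% - 70.3% = 9.0 points), but the SAP's 80% would then not be the power of the test as run.

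**Step 5: the zone where the reading differs.** The observed MOBID-2 difference needed is critical t x sqrt(2/20): 2.024 x 0.316 = 0.64 SD at 0.05 and 2.334 x 0.316 = 0.74 SD at 0.025. A result between these is significant at 0.05 and not under the SAP. The chance of landing there is 7.6% if the true effect is 1.0 SD and 2.5% if there is no effect.

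**Step 6: what a fixed sequence would cost fNIRS.** Assume independent tests and d = 1.0 for fNIRS. Under the split, the chance of an fNIRS claim is 79.3%. Tested second at 0.05, it is 0.869 x 0.869 = 75.5% if the MOBID-2 effect is also 1.0, and 0.338 x 0.869 = 29.4% if the MOBID-2 effect is 0.5.

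**The case against.** The SAP does call pain the primary analysis and never calls fNIRS primary or co-primary. Adjusting across a primary and an important secondary test is valid and does not by itself change their rank. This is a 40-person pilot of preliminary effects; protocol sections 1.0, 2.0 and 6.0 list pain and cortical response as parallel aims, and section 6.0 states a directional expectation for fNIRS. Protecting both tests is a defensible choice, and a secondary label does not by itself imply gatekeeping. Step 6 shows that gatekeeping could cost fNIRS a great deal if the pain effect is modest.

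Most of that stands. It limits the point to an unresolved ranking and the price of the present split. It does not remove the mismatch between Table 1 and the SAP's list of main outcomes, or the absence of a success rule.

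A reader might infer that pain has lost power against the plan. It has not: the 80% was computed at 0.025, and the loss is only relative to an unsplit level. A reader might also infer that the documents lead to opposite conclusions. That is not established. The protocol sets no alpha, so a MOBID-2 p-value of 0.03 is positive under it only if 0.05 is assumed. Nor does the SAP say that fNIRS alone would make the trial positive.

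**Conclusion.** The point holds as an inconsistency in outcome ranking with a moderate, conditional cost. The protocol has one primary outcome and a secondary fNIRS measure; the SAP keeps pain as the primary analysis yet divides alpha equally with fNIRS. Type I error is controlled and the planned power is sound.

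If the overall level is two-sided 0.05, the reading of a Bonferroni 0.025 for two tests that best fits the stated 80%, the sole primary gives up 7.6 points of power at 1.0 SD and about 10 to 11 points at 0.5 to 0.9 SD. The possible difference in interpretation depends on that assumed level for p-values between 0.025 and 0.05, and on an unstated success rule when MOBID-2 is null and fNIRS positive. The documents support saying that such results could be read differently according to the ranking followed, and no more than that.

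**What to change.** Align the SAP with the protocol before unblinding.

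1. State the overall alpha and sidedness, for example two-sided 0.05.
2. Name MOBID-2 change from baseline to the final session as the single primary test, at that full level, and say that trial success rests on it.
3. Test fNIRS as the key secondary outcome in fixed sequence at the same level, only if MOBID-2 is significant. Define the one fNIRS measure to be tested, since section 6.0 describes several channels over bilateral prefrontal and somatosensory cortex and neither document names the summary.
4. Restate the primary power: about 87% at two-sided 0.05 with 20 per group and d = 1.0. If the sponsor means 0.025 to be the overall two-sided level, the figure stays at 79.3%.
5. Tidy section 1.0 of the protocol, where the pain aim sits under secondary objectives.

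Family-wise error stays controlled and no data collection changes. Protocol section 12.0 says data collection is already complete for 20 participants, so the record should show that the change was made without knowledge of results by group.

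The real cost is that fNIRS can no longer support a confirmatory claim when MOBID-2 is not significant; it would then be reported as exploratory (step 6 gives the size). If the sponsor does intend co-primary outcomes, keep the split, change the protocol labels to say so, and state the overall alpha, per-test alpha, sidedness and success rule.
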